# 7.1.3 Immunogenicity Data

Blood samples for immunogenicity analysis will be collected from subjects assigned to the experimental treatment group according to the protocol schedule. Samples will be evaluated for development of nivolumab and ipilimumab Anti-Drug Antibody (ADA) by a validated electrochemiluminescent (ECL) immunoassay and characterized for neutralizing antibodies by validated cell-based assays.

# 7.2 Study Conduct

The following programmable deviations will be considered as relevant protocol deviations.

# **Eligibility:**

- 1) Subjects whose primary anatomical sites other than: oral cavity, oropharynx, hypopharynx and larynx
- 2) Subjects who received prior treatment with systemic anti-cancer therapy within 6 months of randomization
- 3) Subjects who progressed within 6 months of last dose of most recent prior systemic therapy
- 4) Subjects without measurable disease at baseline
- 5) Subjects with ECOG PS > 1 at study entry (last measurement on or prior to randomization)
- 6) Subjects who received prior treatment with an anti-PD-1, anti-PD-L1, anti-PD-L2, anti-CTLA-4 antibody
- 7) Prior treatment with cetuximab or EGFR inhibitors

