3.3.1 Inclusion Criteria

1. Signed Written Informed Consent

- a) Participants must have signed and dated an IRB/IEC approved written informed consent form in accordance with regulatory and institutional guidelines. This must be obtained before the performance of any protocol related procedures that are not part of normal subject care.
- b) Participants must be willing and able to comply with scheduled visits, treatment schedule, and laboratory testing.

2. Target Population

- a) Histologically confirmed head and neck squamous cell carcinoma (SCCHN), from any of the following primary sites only: oral cavity, oropharynx, hypopharynx and larynx.
- b) Must have metastatic or recurrent disease that is not amenable to therapy with curative intent (surgery or radiation therapy with or without chemotherapy). Participants that refuse potentially curative salvage surgery for recurrent disease are ineligible.
- c) No prior treatment with systemic anti-cancer therapy for SCCHN, unless under all of the following conditions:
 - i) Prior chemotherapy was given as adjuvant or neoadjuvant chemotherapy, or part of multimodal (chemo, radiation) treatment for locally advanced disease
 - ii) These treatments must have been completed > 6 months prior to enrollment
 - iii) There is no evidence of disease progression for at least 6 months after completion of systemic treatment.
 - iv) Participants having progression after 2 cycles of induction chemotherapy are excluded.
- d) ECOG Performance Status of 0–1. (See [Appendix 1](#)).
- e) Measurable disease by CT or MRI per RECIST 1.1 criteria (see [Appendix 3](#)); radiographic tumor assessment performed within 28 days prior to first dose.
 - i) Target lesions may be located in a previously irradiated field if there is documented (radiographic) disease progression in that site after the completion of radiation therapy.
- f) Documentation of HPV p-16 status is required for SCCHN tumor of the oropharynx. See [Section 5.6.8](#) for additional guidance. Note: If results are not available, then a sample (tissue on microscopic slides, tissue block or a fresh tissue biopsy in formalin) should be sent to the central laboratory for analysis.
- g) Documentation of tumor cell PD-L1 status by IHC performed by the central lab prior to randomization.

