3.4 Concomitant Treatments

3.4.1 Prohibited and/or Restricted Treatments

The following medications are prohibited during the study (unless utilized to treat a drug related adverse event):

- Any live/attenuated vaccine (eg varicella, zoster, yellow fever, rotavirus, oral polio and measles, mumps, rubella [MMR]) during treatment and until 100 days post last dose.
- Immunosuppressive agents.
- Immunosuppressive doses of systemic corticosteroids (except as stated in section 3.4.2)
- Any concurrent anti-neoplastic therapy (ie, chemotherapy, hormonal therapy, immunotherapy, extensive, non-palliative radiation therapy, or standard or investigational agents for treatment of cancer)
- Surgical resection of tumor
- Any botanical preparation (eg herbal supplements or traditional Chinese medicines) intended to treat the disease under study or provide supportive care. Use of marijuana and its derivatives for treatment of symptoms related to cancer or cancer treatment are permitted if obtained by medical prescription or if its use (even without a medical prescription) has been legalized locally.

Caution should be used regarding the use of herbal medications as there may be as yet unknown interactions with nivolumab and/or ipilimumab. Discontinuation of the use of herbal medications prior to study enrollment is encouraged. Except for the permitted procedures specified as palliative local therapies ([Section 3.4.3](#)), all other radiation therapy or surgery to any tumor lesion is not permitted during study treatment. Participants who require such non-palliative procedures must be discontinued from study treatment.

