3.4.3 Permitted Therapy

Participants are permitted the use of topical, ocular, intra-articular, intranasal, and inhalational corticosteroids (with minimal systemic absorption). Adrenal replacement steroid doses > 10 mg daily prednisone are permitted. A brief (less than 3 weeks) course of corticosteroids for prophylaxis (eg, contrast dye allergy) or for treatment of non-autoimmune conditions (eg, delayed-type hypersensitivity reaction caused by a contact allergen) is permitted.

Regular concomitant use of bisphosphonates and RANK-L inhibitors for prevention or reduction of skeletal-related events in participants with bone metastases is allowed if initiated prior to first dose of study therapy. Prior palliative radiotherapy must have been completed at least 2 weeks prior to treatment.

Prior radiotherapy must have been completed at least 2 weeks prior to randomization. On study palliative radiotherapy is only allowed for treatment of painful bone lesions. Palliative surgical resection of tumor sites is not permitted. Participants requiring palliative radiotherapy should be evaluated for objective evidence of disease progression prior to the initiation of such therapy, particularly if the most recent tumor assessment was more than 4 weeks prior to the start of local therapy. If progression per RECIST 1.1 is identified on any tumor assessments prior to the initiation of palliative local therapy, then participants must either discontinue study drug treatment or they must meet criteria to continue treatment beyond progression ([Section 4.5.6](#)) in order to resume immunotherapy after palliative local therapy.

The potential for overlapping toxicities with radiotherapy and nivolumab/ipilimumab currently is not known; however, anecdotal data suggests that it is tolerable. As concurrent radiotherapy and nivolumab/ipilimumab have not been formally evaluated, in cases where palliative radiotherapy is required for a tumor lesion, then nivolumab/ipilimumab should be withheld for at least 1 week before, during, and 1 week after radiation. Participants should be closely monitored for any potential toxicity during and after receiving radiotherapy, and AEs should resolve to Grade ≤ 1 or baseline prior to resuming study treatment.

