# 6.3 Populations for Analyses

- All Enrolled Subjects: All subjects who signed an informed consent form and were registered into the IVRS.
- All Randomized Subjects: All enrolled subjects who were randomized to either treatment arm.
- All Randomized PD-L1 CPS  $\geq$  20 Subjects: All randomized subjects with PD-L1 CPS  $\geq$  20
- All Randomized PD-L1 CPS  $\geq$  1 Subjects: All randomized subjects with PD-L1 CPS  $\geq$  1.
- All Randomized Tumor PD-L1 expression < 1% Subjects: All randomized subjects with Tumor PD-L1 expression < 1%
- All Randomized PD-L1 CPS < 20 Subjects: All randomized subjects with PD-L1 CPS < 20
- All Randomized GEP  $\geq$  10 Subjects: All randomized subjects with GEP  $\geq$  10.
- All Randomized TMB  $\geq$  7 Subjects: All randomized subjects with TMB  $\geq$  7.
- All Treated Subjects: All subjects who received at least one dose of nivolumab, ipilimumab, cetuximab, cisplatin, carboplatin or 5-FU.
- Treated Subjects with PD-L1 CPS ≥ 20: All subjects who received at least one dose of nivolumab, ipilimumab, cetuximab, cisplatin, carboplatin or 5-FU and have PD-L1 CPS ≥ 20 at baseline.
- All PK Subjects: All subjects with available serum time-concentration data
- Immunogenicity Evaluable Subjects:

- Nivolumab ADA Evaluable Subjects: all treated subjects with baseline and at least
   1 post-baseline pre-infusion nivolumab immunogenicity assessment.
- Ipilimumab ADA Evaluable Subjects: all treated subjects with baseline and at least
   1 post-baseline pre-infusion ipilimumab immunogenicity assessment.
- All PD-L1 CPS Tested subjects: All subjects, randomized or not, who had a tumor biopsy specimen available for tumor cell expression testing. This includes both randomized and screen failure subjects.

Key analyses of study conduct, demographics, and efficacy will be done on the all randomized population and repeated on the randomized PD-L1 CPS  $\geq$  20 population. Subjects in these analyses will be grouped as assigned at randomization.

Key analyses of exposure and safety will be done on the all treated population and repeated on the treated PD-L1 CPS  $\geq$  20 population. Subjects in these analyses will be grouped by treatment received rather than treatment assigned at randomization. Treatment arm received will be equal to treatment arm as randomized, unless the subject received the non-assigned regimen for all doses.

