#### On-study:

- 8) Subjects receiving concurrent antineoplastic therapy (i.e., chemotherapy, hormonal therapy, immunotherapy, surgery for tumor resection\*, radiation therapy directed at target lesions) while on study therapy (Surgery has to be for tumor resection. Tumor biopsy, for example, would not count)
- 9) Subjects whose "as treated" arm different than their as randomized arm (subjects who received the wrong treatment, excluding the never treated)

The Relevant Protocol Deviations will be summarized based on the "all randomized" and "PD-L1 CPS  $\geq$  20" populations, by treatment group and overall. A listing of all relevant protocol deviations will be provided.

Enrollment by country and site, and enrollment by month will be summarized and listed for all enrolled subjects.

A by-subject listing of batch numbers for all treated subjects will be provided.

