# 7.5.7 Supportive Analyses of Overall Survival

The following OS sensitivity analyses will be conducted in all randomized subjects:

- 1) Delayed effect of immunotherapy interventions may cause a late separation in the OS KM curves and non-proportional hazards. OS will be compared between treatment groups via two-sided stratified weighted log-rank test among subjects. The two-sided stratified weighted log-rank p-value will be reported using G (rho = 0, gamma = 1) weights, in the terminology of Fleming and Harrington.
  - The Fleming Harrington test can be unstable, so it is possible, though uncommon, that the p-value for this trial will not be estimable.
  - Further, Max-combo testing and estimating procedure might be applied.
- 2) A multivariate Cox regression model will be used in order to estimate the treatment effect after adjustment for possible imbalances in known or potential prognostic factors. The factors used in the randomization, which, by definition, will be balanced across treatment groups, will still be included in the model as stratification factors. However, all additional factors will be incorporated as covariates. The additional factors, which are all measured at baseline, will include, but not limited to:
  - a. ECOG PS  $(0, \ge 1)$
  - b. SEX (Male, Female)
  - c. AGE

The level of the covariate normally associated with the worst prognosis will be coded as the reference level. The hazard ratio associated with treatment and with each of the baseline covariates will be presented along with associated  $100*(1-\alpha)\%$  CIs (adjusted for interim).

- 3) OS using stratification factors as obtained from the baseline CRF pages (instead of IRT). The hazard ratio associated with treatment will be presented along with the associated two-sided 100\*(1- α)% CI (adjusted for interim). This analysis will be performed only if at least one stratification variable/factor at randomization (as per IRT) and baseline are not concordant for at least 10% of the randomized subjects.
- 4) OS using an un-stratified log rank test. The hazard ratio associated with treatment will be presented along with the associated two-sided  $100*(1-\alpha)\%$  CIs (adjusted for interim).
- 5) OS for subjects with no relevant protocol deviations. This analysis will be conducted only if there are more than 10% subjects with relevant protocol deviations. The hazard ratio

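### Two of the SAP's relevant protocol deviations (systemic-therapy washout and on-study radiotherapy) are defined differently from the protocol rules they check, so deviation counts may be misstated, mostly downward

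*SAP*

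**What the plan says.** **Washout.** Under its Eligibility heading, SAP 7.2 item 2 lists "Subjects who received prior treatment with systemic anti-cancer therapy within 6 months of randomization" as a relevant deviation. Protocol 3.3.1, criterion 2.c.ii, says of permitted prior systemic treatments: "These treatments must have been completed > 6 months prior to enrollment". SAP 6.3 defines enrolled subjects as "All subjects who signed an informed consent form and were registered into the IVRS". Protocol 4.4 places randomization after that step.

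**On-study radiotherapy.** SAP 7.2 item 8 lists concurrent antineoplastic therapy and describes its radiation component as "radiation therapy directed at target lesions". Protocol 3.4.1, after excepting the palliative local therapies of 3.4.3, states that "all other radiation therapy or surgery to any tumor lesion is not permitted during study treatment". Protocol 3.4.3 states the exception: "On study palliative radiotherapy is only allowed for treatment of painful bone lesions".

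**Use of the flags.** SAP 7.2 summarizes relevant deviations by arm and overall, in all randomized subjects and in the CPS ≥ 20 population, with a listing. SAP 7.5.7 item 5 repeats the OS analysis in subjects without relevant deviations, under a condition: "This analysis will be conducted only if there are more than 10% subjects with relevant protocol deviations".

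**The concern.** A programmed deviation should identify the people who broke the rule it stands for. Item 2 starts its clock at a later date than the protocol does. Item 8 sorts radiotherapy by target-lesion status, whereas the protocol sorts it by palliative intent and painful bone site. Neither change is explained.

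At stake are the accuracy of the deviation tables and the decision whether OS sensitivity analysis 5 is run. If it is run, missed violators also stay in a set described as free of relevant deviations.

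**Working it through.** The plan gives no figure to reproduce here. The check is a comparison of rules plus simple arithmetic.

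**1. Washout clocks**

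Let c be the days from the end of prior systemic therapy to enrollment, and g ≥ 0 the days from enrollment to randomization. SAP section 8 sets 1 month at 30.4375 days, so 6 months = 6 × 30.4375 = 182.625 days.

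- The protocol is breached if c ≤ 182.625.
- SAP item 2 flags if c + g ≤ 182.625.
- Missed violators satisfy 182.625 − g < c ≤ 182.625, a band g days wide.
- A false flag would need c > 182.625 and c + g ≤ 182.625, which is impossible when g ≥ 0.

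The documents give no distribution of g, so the values below are assumptions. Protocol 3.1 requires the central PD-L1 result before randomization, so some delay is built in.

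| Assumed g (days) | Missed band (days) | False-flag band (days) |
|---|---|---|
| 0 | 0 | 0 |
| 7 | 7 | 0 |
| 14 | 14 | 0 |
| 28 | 28 | 0 |

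Example: therapy ended 5.5 months before enrollment (5.5 × 30.4375 = 167.4 days) and randomization followed 21 days later. Then c = 167.4 ≤ 182.625, a breach. But c + g = 188.4 > 182.625, so there is no flag.

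**2. Radiotherapy rules side by side**

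| On-study radiotherapy | Protocol 3.4.1 and 3.4.3 | SAP item 8 |
|---|---|---|
| Non-target lesion, not bone | Not permitted | Not flagged |
| Target lesion, not bone | Not permitted | Flagged |
| Painful bone lesion, palliative, non-target | Permitted | Not flagged |
| Painful bone lesion, palliative, target | Permitted | Flagged |

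The first and last rows disagree. Item 8 also counts any surgery for tumor resection without limiting it to target lesions, although protocol 3.4.1 treats radiation and surgery in the same sentence.

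**3. The 10% condition**

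SAP 7.5.7 applies to all randomized subjects, about 930. Since 0.10 × 930 = 93, the analysis runs at 94 or more (94/930 = 10.1%). Correcting the definitions does not move this threshold; only the count compared with it can change.

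| True deviators (assumed) | Net error that would change the decision |
|---|---|
| 70 (7.5%) | overcount of 94 − 70 = 24 |
| 100 (10.8%) | undercount of 100 − 93 = 7 |
| 112 (12.0%) | undercount of 112 − 93 = 19 |
| 140 (15.1%) | undercount of 140 − 93 = 47 |

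No deviation counts are given, so these rows show only what it would take.

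**The case against.** The strongest reply is that SAP 7.2 declares a selected list of programmable deviations and does not claim to mirror every protocol rule. That stands for items that are absent. For example, item 2 does not test the setting required by criterion 2.c.i ("Prior chemotherapy was given as adjuvant or neoadjuvant chemotherapy, or part of multimodal (chemo, radiation) treatment for locally advanced disease"), and the 2-week prior-radiotherapy washout has no item. A reader might call these errors, but a declared selection may leave rules out. The reply does not cover items 2 and 8: the sponsor chose to check these two rules and then stated them differently.

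Randomization is also a single, clean time zero, whereas the protocol allows re-enrollment, so one person can have more than one enrollment date. That is a practical point, met by specifying which date to use.

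On item 8, the list is limited to what can be programmed, and the documents do not show that the CRF records lesion site, pain or palliative intent. SAP Appendix 2 mentions a radiotherapy page only in connection with dates. The protocol's wording is not uniform either: a bullet in 3.4.1 bars extensive, non-palliative radiation, 3.4.3 confines palliative radiation to painful bone lesions, and 3.4.3 later speaks of palliative radiation to a tumor lesion generally. This limits how exact the fix can be but does not justify the target-lesion criterion.

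Three stronger readings are tempting and not supported:

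- **That the 10% trigger is wrong.** The threshold is clear, and nothing shows the count crossing from 93 to 94 or back.
- **That permitted cases are flagged in general.** The washout rule cannot do this. It happens only for a painful bone lesion that is also a target lesion, probably an uncommon case: protocol 5.4 uses bone as its example of a non-target organ, although Appendix 3 does not bar bone target lesions.
- **That four weeks of violations are missed.** The 28-day windows in the protocol govern particular assessments before first dose, not the gap from enrollment to randomization.

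**Conclusion.** The mismatch is in the text and holds for both items. Item 2 can only undercount, by a band as wide as the enrollment-to-randomization gap. Item 8 undercounts prohibited radiation to non-target, non-bone lesions and overcounts one narrow permitted case. The net error is therefore likely to be mostly downward, but its size cannot be computed because neither deviation counts nor the gap distribution is given.

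The consequence is limited to the deviation summaries and listing, and to whether OS sensitivity analysis 5 is run and whom it excludes. Both primary OS comparisons use stratified log-rank tests in randomized populations (SAP 7.5.6) and do not use these flags, so alpha, power and the primary estimates are untouched. This is a minor point, worth correcting because it is cheap. No view is taken on which radiotherapy rule is clinically right.

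**What to change.** - **Item 2:** measure from the enrollment date, taking the latest one for anyone re-enrolled, and flag prior systemic therapy not completed more than 6 months before that date, as criterion 2.c.ii requires.
- **Item 8:** reconcile the radiotherapy wording with protocol 3.4.1 and 3.4.3, dropping the target-lesion criterion as far as the CRF fields allow. The sponsor should first confirm that lesion site and palliative intent are captured. If they are not, or if a narrower rule is intended, the SAP should say so and give the reason.

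The cost is two SAP lines and minor reprogramming. Item 2 is a one-line change; the effort for item 8 depends on the CRF check. The reported deviation rate may rise slightly. The 10% condition can stay as written.

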#### On-study:

- 8) Subjects receiving concurrent antineoplastic therapy (i.e., chemotherapy, hormonal therapy, immunotherapy, surgery for tumor resection\*, radiation therapy directed at target lesions) while on study therapy (Surgery has to be for tumor resection. Tumor biopsy, for example, would not count)
- 9) Subjects whose "as treated" arm different than their as randomized arm (subjects who received the wrong treatment, excluding the never treated)

The Relevant Protocol Deviations will be summarized based on the "all randomized" and "PD-L1 CPS  $\geq$  20" populations, by treatment group and overall. A listing of all relevant protocol deviations will be provided.

Enrollment by country and site, and enrollment by month will be summarized and listed for all enrolled subjects.

A by-subject listing of batch numbers for all treated subjects will be provided.

#### 7.3 Study Population

Analyses in this section will be tabulated for all randomized subjects by treatment group as randomized, unless otherwise specified.

# 7.3.1 Subject Disposition

The total number of subjects enrolled (randomized or not randomized) will be presented along with the reason for not being randomized. This analysis will be performed on the all enrolled subjects population only.

Number of subjects randomized but not treated along with the reason for not being treated will be tabulated by treatment group as randomized.

Number of subjects who discontinued study treatment along with corresponding reason will be tabulated by treatment group as treated. Reason for discontinuation will be derived from subject status CRF page. This analysis will be performed only on the all treated subjects population.

A by-subject listing for all treated subjects will be provided showing the subject's off treatment date and whether the subject continue in the treatment period/study along with the reason for going off treatment period/study. A by-subject listing for all enrolled subjects will also be provided, showing whether the subject was randomized/treated along with the reason for not being randomized/treated.

#### 7.3.2 Demographics and Other Baseline Disease Characteristics

The following demographic and baseline disease characteristics will be summarized and listed by treatment group as randomized:

- Age (continuous)
- Age categorization ( $< 65, \ge 65 \text{ and } < 75, \ge 75 \text{ and } < 85, \ge 85, \ge 75, \ge 65$ )
- Sex (Male vs. Female)
- Race (White, Black or African American, Asian, Other)
- Ethnicity (Hispanic/Latino and Not Hispanic/Latino)
- Region (North America, EU, Asia, Rest of World)
- Country by geographic region
- Baseline ECOG performance status
- Tobacco use (Never, Former, Current, Unknown)
- Alcohol use
- Disease stage at study entry (locally recurrent, locally recurrent and metastatic, metastatic)
- Disease stage at initial diagnosis (stage I, II, III, IVA, IVB, IVC)
- TNM Classification at initial diagnosis
- Time from initial disease diagnosis to randomization (< 1 year,  $\geq$  1 year)
- Sites of primary tumor per investigator
- Subsites of diseases per investigator
- Sites of diseases (all lesions) per BICR
- Number of disease sites per subject (all lesions) per BICR
- Number of target lesions, non-target lesions and disease sites at baseline as per BICR
- Tumor burden: sum of the diameters of target lesions at baseline per BICR

- Tumor burden: sum of the diameters of target lesions at baseline per investigator
- HPV p-16 status per CRF
- Tumor cell PD-L1 proportion score (TPS) per CRF
- PD-L1 CPS
- CNS metastasis

Summary table (cross-tabulation) by treatment group for stratification factor will be provided to show any discrepancies between what was reported through IRT vs. CRF at baseline. This summary will be performed based on all randomized subjects.

